8.3.8 Hy's law

Cases where a patient shows elevations in liver biochemistry may require further evaluation and occurrences of AST or ALT $\geq 3 \times \text{ULN}$ together with TBL $\geq 2 \times \text{ULN}$ may need to be reported as SAEs. Please refer to [Appendix E](#) for further instruction on cases of increases in liver biochemistry and evaluation of Hy's Law.

8.3.9 Disease progression

Disease progression can be considered as a worsening of a patient's condition attributable to the disease for which the IP is being studied. It may be an increase in the severity of the disease under study and/or increases in the symptoms of the disease. The development of new or progression of existing metastasis to the primary cancer under study should be considered as disease progression and not an AE. Events which are unequivocally due to disease progression should not be reported as AEs during the study.

8.3.10 New cancers

The development of a new cancer should be regarded as an SAE. New cancers are those that are not the primary reason for the administration of the study treatment and have been

identified after the patient's inclusion in this study. They do not include metastases of the original cancer.

8.3.11 Deaths

All deaths that occur during the study, or within the follow-up period after the administration of the last dose of study drug, should be reported as follows:

- Death clearly resulting from disease progression should be communicated to the study monitor at the next monitoring visit and should be documented in the eCRF on the Death page. It should not be reported as an SAE.
- When death is not clearly due to PD of the disease under study, the AE causing the death should be reported to the study monitor as an SAE within 24 hours. It should also be documented on the Death page in the eCRF. The report should contain a comment regarding the co-involvement of PD, if appropriate, and should assign a single primary cause of death together with any contributory causes
- Deaths with an unknown cause should always be reported as SAEs, but every effort should be made to establish a cause of death. It should also be documented in the Statement of Death page in the eCRF. A post-mortem may be helpful in the assessment of the cause of death, and if performed a copy of the post-mortem results (with translation of important parts into English) should be forwarded to an AstraZeneca representative within the usual time frames.

Deaths occurring after the protocol defined safety follow-up period after the administration of the last dose of study drug should be documented on the Death page. If the death occurred as a result of an event that started after the defined safety follow-up period and the event is considered to be due to a late onset toxicity to study drug, then it should also be reported as an SAE.

8.3.12 Adverse events of special interest

An AESI is one of scientific and medical interest specific to understanding of the IP and may require close monitoring and rapid communication by the Investigator to the Sponsor, or delegate. An AESI may be serious or non-serious. The rapid reporting of AESIs allows ongoing surveillance of these events in order to characterize and understand them in association with the use of this IP.

Please refer to the modular-specific appendices for AESIs to be followed.

8.3.13 Safety data to be collected following the primary DCO of the study

For patients continuing to receive treatment after primary DCO and database closure, it is recommended that the patients continue the scheduled site visits and Investigators monitor the patient's safety laboratory results prior to and periodically during treatment in order to manage AEs in accordance with the Dose Modification and Toxicity Management Guidelines (see

Section 8.4.5). All data after the primary DCO and database closure will be recorded in the patient notes but, with the exception of SAEs, will not otherwise be reported for the purposes of this study.

All SAEs that occur in patients still receiving treatment (or within the 90 days following the last dose of treatment) after the primary DCO and database closure must be reported as detailed in Section 8.4.1.

8.4 Safety reporting and medical management

8.4.1 Reporting of serious adverse events

All SAEs have to be reported, whether or not considered causally related to the IP, or to the study procedure(s). All SAEs will be recorded in the eCRF.

If any SAE occurs in the course of the study, then Investigators or other site personnel will inform the appropriate AstraZeneca representatives within one day i.e., immediately but **no later than 24 hours** of when he or she becomes aware of it.

The designated AstraZeneca representative works with the Investigator to ensure that all the necessary information is provided to the AstraZeneca Patient Safety data entry site **within 1 calendar day** of initial receipt for fatal and life-threatening events **and within 5 calendar days** of initial receipt for all other SAEs.

SAE information will be sent via secure e-mail connection or via fax. The Innovations Safety Department standard paper SAE Report Form, with supporting relevant source documents (e.g., history and physical [H&P], hospital discharge summary, autopsy report when available, results of relevant diagnostic tests completed to evaluate the event), will be attached and sent via:

- Secure email (Innovations SAE mailbox: PPD [redacted])

or

- Fax (Innovations safety fax number): PPD [redacted]

Transmission of the SAE Report Form should be confirmed by the site personnel submitting the report.

Follow-up information for SAEs and information on non-serious AEs that become serious should also be reported to Innovations Safety Department as soon as it is available; these reports should be submitted using the Innovations SAE Report Form. The detailed SAE reporting process will be provided to the sites in the SAE reporting guidelines contained in the study reference manual. The Innovations Medical Monitor works with the Investigator to ensure that all the necessary information is provided to the Innovations Safety Department

within 1 calendar day of initial receipt of the information for fatal and life-threatening events and **within 5 calendar days** of initial receipt of the information for all other SAEs.

For fatal or life-threatening AEs where important or relevant information is missing, active follow-up is undertaken immediately. Investigators or other site personnel will inform AstraZeneca representatives of any follow-up information on a previously reported SAE within one calendar day i.e., immediately but **no later than 24 hours** of when he or she becomes aware of it.

Investigators must report SAEs and follow-up information to their responsible IRB according to the policies of the responsible IRB. For fatal or life-threatening AEs for which important or relevant information is missing, active follow-up is undertaken immediately.

AstraZeneca, or their representatives, will provide Regulatory Authorities, Ethics Committees, and Principal Investigators with clinical safety updates/reports according to local requirements.

Full details of the AE reporting process are provided in the Safety Handling Plan for the study.

For further guidance on the definition of a SAE, see [Appendix B](#) of the core Clinical Study Protocol.

8.4.2 Pregnancy

Conception must be avoided during paternal exposure to AZD4635. If a pregnancy in the female partner of a male patient is reported, the investigator should inform the Innovations Safety Department within 24 hours of learning of the pregnancy. Exception to this is if the pregnancy is discovered before the study subject has received any study drug. Abnormal pregnancy outcomes (e.g., spontaneous abortion, fetal death, stillbirth, congenital anomalies, ectopic pregnancy) are considered SAEs.

8.4.2.1 Paternal exposure to AZD4635

Information on the pregnancy of a patient's partner must be obtained directly from the patient's partner. Therefore, prior to obtaining information on the pregnancy, the Investigator must obtain the consent of the patient's partner.

Pregnancy of a patient's partner is not considered to be an AE. However, outcome of all pregnancies (spontaneous miscarriage, elective termination, ectopic pregnancy, normal birth, or congenital abnormality) occurring from the first date of dosing until 3 months (unless specified differently in relevant module) after dosing should, if possible, be followed up and documented.

Male patients should use condoms with female partners during the study and for 12 weeks (3 months or as specified in relevant module) after the last dose of AZD4635, and refrain from donating sperm from the start of dosing until 24 weeks (6 months) after discontinuing study treatment. If not done previously, storage of sperm prior to receiving AZD4635 will be advised to male patients with a desire to have children. See relevant module for module-specific information.

It is not currently known whether AZD4635 affects fertility in humans.

AstraZeneca should be notified of any pregnancy that occurs in partners of male patients during participation in studies of AZD4635.

8.4.3 Overdose

Any dose of AZD4635 in excess of 110% of the dose per cycle of treatment specified according to the protocol will constitute an overdose, unless associated with an AE, in which case any dose in excess of the dose specified according to the protocol will constitute an overdose. There is currently no known antidote to AZD4635, and the treatment of overdose should be supportive for the underlying symptoms. Please refer to relevant module to see module-specific overdose guidance.

- An overdose with associated AEs is recorded as the AE diagnosis/symptoms on the relevant AE modules in the eCRF and on the Overdose eCRF module.
- An overdose without associated symptoms is only reported on the Overdose eCRF module

If an overdose of an AstraZeneca study drug occurs in the course of the study, then the Investigator or other site personnel will inform appropriate AstraZeneca representatives immediately, or **no later than 24 hours** of when he or she becomes aware of it.

The designated AstraZeneca representative works with the Investigator to ensure that all relevant information is provided to the AstraZeneca Patient Safety data entry site.

- For overdoses associated with a SAE, the standard reporting timelines apply (see Section 8.3.2). For other overdoses, reporting must occur within 30 days.

8.4.4 Medication error

If a medication error occurs in the course of the study, then the Investigator or other site personnel will inform the appropriate AstraZeneca representatives within 1 day i.e., immediately but **no later than 24 hours** of when he or she becomes aware of it.

The designated AstraZeneca representative works with the Investigator to ensure that all relevant information is completed within 1 calendar day (initial fatal/life-threatening or follow-up fatal/life-threatening) or 5 calendar days (other serious initial and follow-up) if there is an SAE associated with the medication error (see Section 8.3.2) and within 30 days for all other medication errors.

The definition of a medication error can be found in [Appendix B](#).

8.4.5 Management of AZD4635-related toxicities

AZD4635 management and discontinuation guidelines for non-hematologic toxicities (except hypertension) are shown in [Table 9](#). Inpatient dose re-escalation is not permitted. AZD4635 dose reduction guidelines are in Section 6 of the study-specific modules.

If a patient experiences a clinically significant and/or unacceptable toxicity not attributable to the disease or disease-related processes under investigation, dosing will be interrupted or the dose reduced and supportive therapy administered, as required. If the toxicity resolves or reverts to \leq CTCAE Grade 2 within 2 treatment weeks and the patient is showing clinical benefit per the Investigator, treatment with AZD4635 may be restarted. If the toxicity does not resolve to \leq CTCAE Grade 2 after 2 weeks of treatment then the patient should be withdrawn from the study and observed until resolution of the toxicity. Maximum drug holiday allowed is 2 weeks for non-immune-mediated toxicity.

Table 9 AZD4635 dose modifications and discontinuation criteria for non-hematologic toxicities (except hypertension)

NCI CTCAE Toxicity Grade	Action
Grade 1 or 2	None required
Grade 3 or 4 and/or clinically significant^a	Hold AZD4635
Toxicity resolved to Grade 1, Grade 2, or baseline <14 days	Restart AZD4635 at 1 dose level reduction
Toxicity remains Grade 3 to 4 or is clinically significant ^a >14 days	Discontinue AZD4635
Recurrence of Grade 3	Reduce 1 more dose level if module-specific guidance allows or if not discontinue AZD4635
Recurrence of Grade 3 cardiac event^a	Discontinue AZD4635
Recurrence of Grade 4	Discontinue AZD4635

^a Includes significant change in CK/CK-mb ratio (relative index >5%), increases in heart rate of +25 bpm (up to 100 to 125 bpm) for more than 24 hours or increase in heart rate >125 bpm for more than 12 hours), QTc prolongation >500 ms.

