7 DISCONTINUATION OF TREATMENT AND PATIENT WITHDRAWAL

7.1 Discontinuation of study treatment

Patients that discontinue 1 study drug may remain on the study and receive other study drug(s) as long as they are continuing to derive clinical benefit (see Section 8.4.6). Patients may be discontinued from study drug(s) in the following situations:

- Patient decision. The patient is at any time free to discontinue treatment, without prejudice to further treatment.
- Any AE that, in the opinion of the Investigator or AstraZeneca, contraindicates further dosing or meets the criteria for discontinuation as defined in the dose modification guidance or prescribing information for the study drug(s).
- Investigator decision or severe non-compliance with the Clinical Study Protocol
- Confirmed disease progression unless, in the opinion of the Investigator, the patient is still receiving clinical benefit. Patients will continue study treatment until objective disease progression, or beyond RECIST 1.1 defined progression if patient is receiving clinical benefit, as judged by the Investigator and in the absence of discontinuation criteria. Tumor assessment must continue while patient continues to receive study treatment as per Section 8.1.1.

- Patients incorrectly initiated on study drug(s) (e.g., patient is determined to have met one or more of the exclusion criteria for study participation at study entry and continuing investigational therapy might constitute a safety risk)
- Patient started alternative anticancer therapy including another investigational agent
- Patient lost to follow-up

Note that discontinuation from study treatment is NOT the same thing as a complete withdrawal from the study.

See the SoA of the assigned module for data to be collected at the time of treatment discontinuation and follow-up and for any further evaluations that need to be completed. The reason for study drug and combinational agent discontinuation will be recorded in the eCRF.

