7.1.1 Procedures for discontinuation of study treatment

The Investigator should instruct the patient to contact the site before or at the time if study treatment is stopped. Discontinuation of study treatment, for any reason, does not impact the patient's participation in the study. A patient that decides to discontinue study treatment will always be asked about the reason(s) and the presence of any AEs. The date of last intake of study treatment and the combinational agent should be documented in the eCRF. All study treatment should be returned by the patient at his next on-site study visit or unscheduled visit. Patients permanently discontinuing study treatment should be given locally available standard of care therapy, at the discretion of the Investigator.

The patient should continue attending subsequent study visits and data collection should continue according to the study protocol. If the patient does not agree to continue in-person study visits, a modified follow-up must be arranged to ensure the collection of endpoints and safety information. This could be a telephone contact with the patient, a contact with a relative or treating physician, and/or information from medical records. The approach taken should be recorded in the medical records. A patient who agrees to modified follow-up is not considered to have withdrawn consent or to have withdrawn from the study.

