8.2.8.2 Progression-free follow-up visits

Patients who discontinue study treatment prior to the occurrence of objective PD will be followed with PSA samples and CT/MRI/PET and bone scans every 3 months (± 1 week) from the last date of the last tumor response assessment until either: objective PD has been confirmed, withdrawal of consent, until the primary analysis DCO, or until the study or module is terminated by the Sponsor.

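### Section 8.4.5 tells sites to withdraw a patient from the study for unresolved toxicity, where Table 9 and Sections 7.1, 7.1.1 and 8.2.8.2 call for stopping drug and continuing follow-up

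*Protocol*

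**What the plan says.** The paragraph before Table 9 in Protocol Section 8.4.5 covers any clinically significant or unacceptable toxicity not due to the disease. Dosing is interrupted or reduced, and may restart if the toxicity falls to Grade 2 or lower within 2 weeks. If it does not, "then the patient should be withdrawn from the study and observed until resolution of the toxicity".

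Table 9 has a row for the case where "Toxicity remains Grade 3 to 4 or is clinically significant" for more than 14 days. The action in that row is to stop AZD4635. It does not mention leaving the study.

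Other sections deal with what happens once drug is stopped:

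- Section 7.1 lists an adverse event that meets the dose-modification criteria as a reason to stop study drug(s). It adds that "discontinuation from study treatment is NOT the same thing as a complete withdrawal from the study".
- Section 7.1.1: "Discontinuation of study treatment, for any reason, does not impact" the patient's participation. It continues: "The patient should continue attending subsequent study visits and data collection should continue according to the study protocol".
- Section 8.2.8.2: "Patients who discontinue study treatment prior to the occurrence of objective PD will be followed with PSA samples and CT/MRI/PET and bone scans". The interval is 3 months, and this follow-up runs until confirmed objective progression, withdrawal of consent, the primary data cut-off, or termination of the study or module by the sponsor.

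**The concern.** The same clinical event receives two different instructions, and the protocol itself treats the two acts as different. A site dealing with an unresolved toxicity will look first at the toxicity section, and there the running text tells it to take the patient off study.

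If a site acts on that text, PSA sampling and imaging end because of toxicity. Two efficacy analyses depend on data collected after treatment stops:

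- **rPFS and duration of response.** Section 9.4.4 counts progression or death whether or not the patient has left treatment, so it needs scans after treatment. Without them, censoring is tied to toxicity, which is unlikely to be unrelated to prognosis.
- **ORR.** A response needs a confirming scan. A patient removed between the first response and that scan cannot be confirmed as a responder, yet stays in the tumor response population of Section 9.3, which requires only dosing, a baseline tumor assessment and measurable disease.

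**Working it through.** No power, sample size or event calculation applies. The check compares the texts and then asks which endpoints a literal reading could reach.

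**1. The instructions side by side**

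| Place | Trigger | Action |
|---|---|---|
| 8.4.5, paragraph | Not at Grade 2 or lower after 2 weeks | Withdraw from the study; observe until resolved |
| 8.4.5, Table 9 | Still Grade 3 to 4, or clinically significant, beyond 14 days | Stop AZD4635 |
| 8.4.5.1, Table 10 | Hypertension criteria | Stop AZD4635 or study drug |
| 7.1 | Adverse event meeting dose-modification criteria | Stop study drug(s); stated not to equal withdrawal |
| 7.1.1 | Treatment stopped for any reason | Visits and data collection continue |
| 8.2.8.2 | Treatment stopped before objective progression | PSA and scans every 3 months; toxicity is not among the reasons to end them |

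The first row is the outlier. It stands in the current version 6.0 text, and no redaction touches it.

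**2. Does Table 9 always correct the sentence?** No. Table 9 is limited by its title to non-hematologic toxicity other than hypertension, and Table 10 to hypertension. The paragraph covers any toxicity. For a hematologic toxicity it is the only AZD4635 action rule in the core text shown. The modules are not shown.

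**3. rPFS and duration of response.** Section 9.4.4 censors a patient who progresses or dies after 2 or more missed radiologic visits at the last evaluable assessment before them. If scans end for toxicity, even a known later death can become a censored rPFS time. Duration of response takes the PFS censoring date, so it inherits the problem.

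**4. RECIST confirmation.** The first scan is at week 6 (plus or minus 1) and the next is 8 weeks later: 6 + 8 = week 14. Appendix G places confirmation at that next scheduled assessment. Section 8.2.7 requires an end-of-treatment scan only if none was done in the past 2 months. Assuming 2 months is 61 days, 61 / 7 = 8.7 weeks, so no scan is required until 6 + 8.7 = week 14.7 (5 + 8.7 = 13.7 to 7 + 8.7 = 15.7 over the scan window). A week-6 responder who comes off treatment well before week 14 may therefore have no end-of-treatment scan. Under the intended handling there are two routes to confirmation:

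- If the antibody continues, the patient stays on the 8-weekly schedule.
- If all treatment stops, the Section 8.2.8.2 scan, timed "from the last date of the last tumor response assessment until either" one of its listed endpoints is reached, falls at about 6 + 13 = week 19.

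Literal withdrawal closes both.

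**5. PSA response and OS.** A 14-day hold followed by an end-of-treatment visit within 7 days of the decision (Section 8.2.7) puts the end-of-treatment PSA 14 to 14 + 7 = 21 days after the hold began. If the first low value came at least 7 days before the hold, that PSA is at least 7 + 14 = 21 days later and can serve as the second value. For OS, Section 8.2.8.3 lets sites obtain the vital status of patients withdrawn from the study. Neither endpoint is materially exposed.

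**The case against.** The strongest reply is that the protocol already settles the case. Section 7.1 treats an adverse event meeting the dose-modification criteria as a reason to stop drug, Section 7.1.1 keeps the patient in the study whatever the reason for stopping, and toxicity is not among the reasons in Section 8.2.8.2 for ending scans. Section 7.3 describes withdrawal from the study as the patient's own request, and one of its options keeps follow-up procedures. The disputed sentence itself goes on to require observation, which does not fit a complete exit. Table 6 uses the same phrase loosely for patients who need another anticancer agent, so it may be shorthand for being off treatment.

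Most of this stands, and it is why the point is minor. It does not remove the conflict. A site must override an explicit toxicity instruction by reading three other sections, and for hematologic toxicity no table helps. Observation until resolution preserves safety data but does not provide PSA or scans.

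Some stronger readings are tempting, and the documents do not support them:

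- *The plan intends to end efficacy follow-up for toxicity.* Sections 7.1, 7.1.1 and 8.2.8.2 show the opposite intention.
- *The week-19 scan is the only confirmation left.* That is true only if all study treatment stops and no end-of-treatment scan is taken. Sections 7.1 and 8.4.6 allow the partner drug to continue. The end-of-treatment exemption can lapse at week 13.7, before week 14, and the 7-day allowance for that visit can also carry it past the limit. Section 8.2.7 does not forbid an earlier scan.
- *ORR would fall by 5 points.* 1/20 = 5.0 points is the weight of any one responder among about 20. It says nothing about how often this would happen.
- *PSA50 and OS would also be damaged.* Step 5 of the working shows otherwise.

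**Conclusion.** The wording conflict is real and certain on the text: one operative instruction says withdraw from the study where the rest of the core protocol says stop drug and continue follow-up. The harm is conditional on a site following the sentence literally. In that case rPFS and duration-of-response censoring would depend on toxicity, and an early RECIST response could go unconfirmed while the patient remains in the ORR denominator.

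No numerical effect is claimed. The protocol gives no rate of toxicity above Grade 2 lasting more than 2 weeks, and Section 2.3 describes the common adverse events as mostly Grade 1 or 2, so the number affected is unknown and may be zero. All endpoints are analysed descriptively (Section 9.2), so no test or error rate is affected. Severity: minor. The conclusion rests on the core protocol alone. The modules may add dose-reduction detail, but that would leave the contradiction within the core text in place.

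**What to change.** In Section 8.4.5, replace the words that withdraw the patient from the study with: *permanently discontinued from AZD4635, with study follow-up continued per Sections 7.1.1 and 8.2.8*. Keep the clause requiring observation until the toxicity resolves. Leave the handling of the partner drug to Sections 7.1 and 8.4.6 and the module; the toxicity paragraph does not need a partner-drug clause.

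The cost is a one-phrase change, which can go in with the next amendment and its IRB/IEC approval, plus a clarification letter to sites. It adds no visits, procedures or patients beyond those already in the protocol.

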8.1.4 PWCG3 PSA criteria

All patients should have PSA collected **CCI** at screening, at the start of each new treatment cycle, at the end of study treatment, and as indicated in the SoA of each module. PSA **CCI** should also be collected when clinically indicated as per Investigator discretion.

PWCG3 PSA criteria are located in [Appendix I](#).

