
Grade 3 (systolic BP \geq160 mm Hg or diastolic BP \geq100 mm Hg); medical intervention indicated; more than one drug or more intensive therapy than previously used indicated
	
Initiate or maximize BP therapy as per local guidelines.
 
Consider consult with a BP management specialist
	
Increase frequency of monitoring until stabilized to BP $<$150/90 mmHg
	
May continue AZD4635 with optimization of antihypertensive management unless persistent BP-related clinical symptoms.
 
Hold AZD4635 if BP is not decreased to grade 2 within 48 hours after optimum therapy is instituted.
 
If BP is reduced to baseline or Grade 1 within 14 days and considered stable, AZD4635 may be resumed at original dose.
 
Discontinue AZD4635 if BP does not resolve to Grade 1 within 14 days.
 
Discontinue AZD4635 if BP systolic \geq180 mmHg and/or diastolic \geq110 mmHg)
 
Recurrence of Grade 3: Discontinue study drug.

Grade 4 Life-threatening consequences (e.g., malignant hypertension, transient or permanent neurologic deficit, hypertensive crisis); urgent intervention indicated
	
Initiate treatment per local guidelines, including hospitalization, ICU management, and IV therapy as necessary
		
Discontinue AZD4635

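### Section 8.4.5 orders study withdrawal for toxicity not resolved after 2 weeks, whereas Table 9 stops only AZD4635 and Sections 7.1, 7.1.1 and 8.2.8.2 keep such patients in follow-up

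*Protocol*

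**What the plan says.** Section 8.4.5 first describes holding or reducing AZD4635 for clinically significant or unacceptable toxicity. Treatment may restart if the toxicity falls to Grade 2 or lower within 2 weeks. If it does not, "then the patient should be withdrawn from the study and observed until resolution of the toxicity". This sentence is not limited to any class of toxicity.

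Table 9, in the same section, covers non-hematologic toxicity other than hypertension. Its row beginning "Toxicity remains Grade 3 to 4 or is clinically significant", for more than 14 days, has one action: stop AZD4635. Table 10 in Section 8.4.5.1 handles hypertension in the same way: "Discontinue AZD4635 if BP does not resolve to Grade 1 within 14 days".

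On study status, the other sections agree with one another:
- Section 7.1 lets a patient who stops one study drug stay on study and receive the other, and states that "discontinuation from study treatment is NOT the same thing as a complete withdrawal from the study".
- Section 7.1.1 says that stopping treatment for any reason leaves participation unaffected: "The patient should continue attending subsequent study visits and data collection should continue according to the study protocol".
- Section 8.2.8.2 requires PSA, CT/MRI/PET and bone scans every 3 months for patients who stop before objective progression, "until either: objective PD has been confirmed, withdrawal of consent, until the primary analysis DCO", or until the sponsor terminates the study or module. Toxicity is not a stopping condition.
- Section 8.4.6 allows either agent to continue while there is clinical benefit.

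Section 7.3 describes withdrawal from the study as taking in both study drug and assessments.

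**The concern.** One event has two stated outcomes, and the difference is one on which the protocol itself insists. A site that follows Table 9 and Section 7.1.1 stops AZD4635 and keeps scanning. A site that follows the 8.4.5 sentence, and gives withdrawal its Section 7.3 meaning, could end scans and PSA. Section 8.4.5 does not refer to the sections that would correct this reading.

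The endpoint most exposed is ORR. Appendix G requires a response to be confirmed at the next scheduled assessment, 8 weeks later and not under 4 weeks, and a PR followed by a non-evaluable visit counts only as SD or NE. rPFS (Section 9.4.4) counts progression or death even after the patient withdraws from treatment, so early study exit for toxicity would cut short follow-up that the definition calls for. PSA50 is less exposed, because PSA is collected "at screening, at the start of each new treatment cycle, at the end of study treatment". OS is largely protected, because Section 8.2.8.3 provides for obtaining the vital status of withdrawn patients.

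**Working it through.** **1. Text comparison**

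| Place | Trigger | Drug action | Study status |
|---|---|---|---|
| 8.4.5 text | Above Grade 2 after 2 weeks | Implied stop | Withdrawn from study |
| Table 9 | Grade 3-4 or clinically significant, >14 days | Stop AZD4635 | Silent |
| Table 10 | Hypertension not at Grade 1 in 14 days | Stop AZD4635 | Silent |
| 7.1, 7.1.1 | Any treatment discontinuation | Other drug may continue | Stays in study |
| 8.2.8.2 | Stops before objective progression | n/a | PSA and scans every 3 months |

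The tables alone do not contradict the sentence on study status. The direct conflict is with 7.1 and 7.1.1.

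**2. Does the end-of-treatment (EOT) visit rescue confirmation?**

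Assumptions: 28-day cycle (2 cycles = 8 weeks), stop decision on hold day 14, EOT 0 to 7 days later (Section 8.2.7), hold start spread evenly over the interval, follow-up ending at that point.

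- *Scan.* Let the hold start h days after the scan that first shows response. Withdrawal precedes the day-56 confirming scan if h + 14 < 56 (42/56 = 75%) or, with EOT 7 days later, if h + 21 < 56 (35/56 = 62.5%). Section 8.2.7 calls for EOT imaging only if none was done in the past 2 months (about 61 days), so no EOT scan is due in these cases. A patient who stays in the study after a week-6 response is next scanned at week 14 if the partner drug continues, or at about week 19 under 8.2.8.2.
- *PSA.* Let the hold start d days after the first 50% decline. The EOT PSA falls at d + 14 to d + 21 days. It is at least 21 days later for every d from 7 to 27 (21/28 = 75%). For d from 0 to 6 it depends on the EOT day.

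These fractions describe timing only. They are not probabilities that a response is lost.

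**3. Effect of one lost confirmation (exact Clopper-Pearson 95% CI)**

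The synopsis figures reproduce: 5/20 = 25.0% (8.7 to 49.1) and 9/30 = 30.0% (14.7 to 49.4).

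- ORR with one fewer: 4/20 = 20.0% (5.7 to 43.7).
- PSA50 with one fewer: 8/30 = 26.7% (12.3 to 45.9).

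Denominators do not change, because the Section 9.3 response populations need only dosing and baseline data.

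**4. Effect of one early-censored patient on 6-month rPFS**

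Assume exponential rPFS with median 14.9 weeks, the PFS figure in Section 2.3 for the earlier durvalumab combination; using it for Module 2 (oleclumab) is a further assumption. With n = 30, the expected number event-free is 30 × exp(-ln 2 × t / 14.9): 22.7 at week 6, 15.6 at week 14, 10.8 at week 22 and 9.0 at week 26. Rounded, these are 23, 16, 11 and 9. With full follow-up the estimate is 9/30 = 30.0%.

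| Censored just after | Would have been | Kaplan-Meier at week 26 | Shift (points) |
|---|---|---|---|
| Week 6 | Progressed by week 26 | 23/30 × 9/22 = 31.4% | +1.4 |
| Week 14 | Progressed by week 26 | 16/30 × 9/15 = 32.0% | +2.0 |
| Week 22 | Progressed by week 26 | 11/30 × 9/10 = 33.0% | +3.0 |
| Week 6 | Event-free at week 26 | 23/30 × 8/22 = 27.9% | -2.1 |

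**The case against.** The strongest reply is that the rest of the protocol already settles the matter. Section 7.1 draws the distinction in capitals, 7.1.1 applies to discontinuation for any reason, 8.2.8.2 does not list toxicity among its stopping conditions, and 7.3 treats withdrawal as the patient's own act. The disputed sentence also keeps the patient under observation. Data are lost only if a site follows one sentence against several others. This is fair. A reader might infer from 8.4.5 that the protocol ends assessments for these patients; it nowhere says so.

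Nor is 8.4.5 alone in this usage. Table 6 says that a patient who needs another anticancer agent must first leave the study, yet rPFS and OS are defined regardless of further anti-cancer therapy. The phrase may be loose shorthand for coming off treatment. That softens the reading of 8.4.5, but it also means that Table 6 needs the same correction.

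A reader might also infer that the partner drug is lost. Section 8.4.6 allows the other agent to continue, and Appendices K and L, which may hold the partner-drug rules, are not shown, so the documents at hand do not establish this.

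Finally, the impact is conditional. A lost ORR or PSA50 response needs an unconfirmed responder, toxicity lasting over 14 days, a literal-minded site, and a response that would otherwise have been confirmed. Section 2.3 describes the most common events as mostly Grade 1 or 2. The study is descriptive, and the synopsis estimated last patient completed in Q2 2021, while version 6.0 is dated 24 June 2021, so few patients may be left to benefit. All this limits the importance of the point. It does not remove the contradiction.

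**Conclusion.** The contradiction is certain and lies within the core protocol. Its consequence is possible loss of data, not demonstrated bias. The size is unknown, because the protocol gives no rate of toxicity lasting beyond 2 weeks.

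Per affected patient the effect is 5.0 points on ORR (1/20) or 3.3 points on PSA50 (1/30), both small against the stated intervals. For 6-month rPFS, the illustrative cases run from about -2 to +3 points per patient of 30, under an exponential model with an assumed median of 14.9 weeks. A reader who looked only at censoring just after week 6 in a patient about to progress might infer that the shift is always upward and at most 1.4 points. Later censoring gives more, and a patient who would have stayed event-free moves the estimate down, so that bound does not hold.

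The sentence should be corrected because the change is cheap and the exposed endpoints include a primary one. The point does not call the design into question.

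**What to change.** In Section 8.4.5, replace the instruction to withdraw the patient with: *AZD4635 should be permanently discontinued; the patient remains in the study for follow-up per Sections 7.1.1, 8.2.8.2 and 8.2.8.3, and may continue the combination agent if Section 7.1 and the module allow.* Keep the requirement to observe the patient until the toxicity resolves.

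In Table 6, change the similar wording to withdrawal from study treatment, since rPFS and OS are followed regardless of further anti-cancer therapy.

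The cost is one sentence, one table entry and a notice to sites. The follow-up visits already exist, so no procedures are added. Safety is not weakened, because AZD4635 still stops at the same point.
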